5.8 Withdrawal of Subjects

Participants who wish to withdraw may do so at any time without affecting their medical care or participation in any other study. Participants will be informed of any new information during the course of the study which may affect their condition or influence their willingness to continue in this study. Finally, based on decisions made by the Principal Investigator, participants may be taken out of the study because of unanticipated circumstances such as extreme distress. That is, they may be withdrawn from the study if we judge that participating is not in their best interest.

6.0 Protection of Human Subjects

Protection of Human Subjects

Risk to Participants

Human Subjects Involvement and Characteristics. The purpose of this study is to assess the feasibility and acceptability of Cognitive-Behavioral Therapy for Loneliness for Substance Use Disorders (CBT-L/SUD) among Veterans with SUD who are lonely. After an initial refinement phase during which 6 Veterans will complete the study protocol, a total of 30 participants will be recruited across the US and randomized to receive either CBT-L/SUD (n = 15) or Cognitive-Behavioral Therapy for Substance Use Disorders (CBT-SUD; n = 15).

According to 2018 data from the National Survey of Drug Use and Health, 92.9% of respondents who had ever served in the military and had SUD were men. We expect to have a greater number of women compared to this proportion given that loneliness is more common among women and given increased recruitment of women. SUD prevalence increases with age as those with SUD who had ever served in the military was least common among ages 18-25 (1.3%) and 26-34 (6.8%) and most common among those 35-49 (16.4%) and 50+ (52.1%). We expect there to be relatively greater proportions of younger age and older age groups (rather than middle age groups) because loneliness is more common among those age groups.

Source of Materials. Study materials will include self-report questionnaires. The materials will be collected for study purposes only. Information collected will be stored in a locked filing cabinet in a locked office at the study sites that can only be accessed by members of the study team. *All electronic data* will be stored on VA Informatics and Computing Infrastructure (VINCI) project servers. Only approved study team personnel who will be involved in data entry, management and analyses will be granted access to this data. All computers are password protected.

Potential risks.

Psychological distress. Anticipated risks to the participants from assessment procedures and therapy are minimal; however, participants may experience psychological distress, frustration, and/or fatigue. The semi-structured interviews, assessments associated with the intervention, and therapy sessions may encourage participants to recall personal events and life stressors that may evoke distress. Additionally, confidentiality may need to be breached if a participant poses a threat to him or herself or others, including child abuse.

Adequacy of Protection from Risk Recruitment and Informed Consent.

All research staff will have completed appropriate and up-to-date training in research, research ethics and the proper conduct of research that includes common issues related to recruitment and informed consent.

Participants will be recruited using Internet social media websites, select web portals, and data accessed through the Corporate Data Warehouse. Advertisement will nationally target Veterans using opioids and who may be lonely. Targeted recruitment of women Veterans and Veterans of ethnic/racial minority status will also be used for advertisements. All sites will send participants to a study landing page, which serves as a central location for potential participants to follow-up with the study team via phone or completing and submitting an online form. Recruitment and informed consent procedures were designed to ensure patients do not feel like participation is required. Potential participants unable to understand the informed consent process will be excluded from participating. Screening interviews will be completed initially over the telephone (using a script) to assess eligibility criteria. Verbal consent will be obtained at this time to complete the screening. Participants screening positive for exclusion criteria will not be included in the study. For eligible and interested participants, a research coordinator will review the consent form and complete a brief questionnaire to ensure the potential participant understands the study. Verbal consent will be completed with procedures used by the PI that have been approved by our local IRB. Specifically, once eligibility is confirmed through screening, each of the essential elements of informed consent will be described to the Veteran to which they can provide verbal consent. The Veteran will be enrolled following consent.

Protection Against Risk.

Psychological distress. The potential risks are negligible. There are no known risks associated with interview procedures. Participants will be informed that they may feel slightly uncomfortable discussing some of their symptoms. Mild discomfort may be likely during the intervention session; however, this is unlikely to have a serious negative impact on the participant's well-being. Participants will be told they can withdraw from the study at any time. Participation or withdrawal from the study will not affect any benefits to which they are otherwise entitled. Special precaution will be taken to safeguard confidentiality. During assessments, if the interviewer is concerned about thoughts and planning of a suicide attempt, the interviewer will ask two follow-up questions: Do you have a desire to kill yourself that you think you might act on and Do you have a plan for killing yourself and intend to carry the plan out? With this information and available suicide assessment measures, the interviewer will evaluate the severity of the participant's suicide risk. If the participant is deemed to be at imminent risk, a safety plan will be initiated. All study staff will receive adequate training in suicidal ideation and risk assessment, and all work will be supervised by Drs. [name], who is a licensed clinician.

If the interviewer is concerned about imminent risk, procedure for warm transfers to the National Suicide Prevention Lifeline ([name]; 988 by July, 2022). Emergency procedures will be initiated if patients are determined to be at imminent risk for suicide using the risk assessment described above. Participants determined to be at risk will be asked if they are willing to be transferred to the National Suicide Prevention Lifeline. Hotline responders are well trained in emergency procedures and have working protocols for locating callers and initiating rescues. All telephone sessions will be conducted using protocols to ensure that the clinicians' telephone is set up for transfers to the Crisis Line. Calls can be transferred with a four step process.

Warm Transfer Process

1. Press the **conference/add caller** button.
2. Dial [name] press option 1 and a Crisis Line responder will answer.
3. Describe the participants risk and provide name and telephone number.
4. Pressing the **conference/merge calls** button and participants will be linked with Crisis Line

It is possible that participants may refuse to be transferred to the Crisis Line or hang up. As a result, participants will be asked to use a landline so that the number can be tracked to an address if emergency services are needed. For participants who only have a cell phone,

Interviewers will begin each session by asking the participant for the address from which they are calling so that the clinician can send help if it is needed. Because participants may give a false address, clinicians will consult with Lifeline responders who have a protocol for emergency responses for cell phone callers.

For participants that have a lower risk than imminent for suicide at baseline, our crisis plan will be consistent with guidelines employed by [name] as well as by the DoD/VA for people at low acute risk for suicide. This involves the following, which may or may not already be in place at the time the participant is deemed at low acute risk: (1) consider consultation with behavioral health specialty, (2) discuss safety and restriction of access to lethal means, (3) treat mental health and medical conditions, (4) address psychosocial needs, (5) encourage social support from friends, family, and/or community, (6) continue monitoring patient status and reassess risk in follow-up contacts, and (7) document risk assessment.

The Project Coordinator, research staff, and Research Therapists will receive extensive training in conducting screening for suicide risk assessment by [name] in consultation with Drs. [name], [name], and [name]. In addition, the Project Coordinator and Research Therapist will complete training webinars and extensive test-outs for fidelity.

Breach of Confidentiality. Statistical electronic data files will be kept VINCI project servers maintained by VINCI OI&T personnel and only summarized data without protected health information (PHI) will be downloaded from VINCI to local storage media. Research staff will use an audited VINCI download utility to move summarized data for reports, presentations and publications from VINCI servers to local storage media. The VINCI download utility provides an audit path including a copy of the downloaded material. The data extraction tool will be adapted for use with software directly available on the VINCI platform (e.g. Microsoft Word and Excel) and study data will be stored and maintained on VINCI. All study team personnel with access to sensitive patient data will stay current on their VA approved information security training and VA approved privacy policy training.

Data Safety & Monitoring Plan

Data Safety. To ensure safety of participants in the study proposed and validity and integrity of data collected, the PI ([name]) will oversee all data and safety monitoring functions and the research team will be advised that he will be the primary contact overseeing these activities. The investigators will meet regularly to monitor study progress and discuss the implementation of monitoring procedures. The PI will also meet regularly with the research staff to review monitoring procedures and ensure all efforts are being taken to minimize risks to participants. We will have an independent Data Safety & Monitoring Board (DSMB), appointed by HSR&D to help monitor safety issues. As indicated below, the PI will track all negative outcomes and incidents as well as conduct interim data analysis every 6 months after the study has started. The study design will be significantly modified (and even screening stopped) on the suggestion of the DSMB if the study is creating potential harm to our participants.

The PI will regularly oversee all aspects of the study, including participant recruitment, informed consent, data collection, management, and analysis, as well as regularly assess the risk/benefit ratio associated with participation in the study. All research staff will participate in an intensive

training to help them understand the importance of reducing the risk for participants and learning how to recognize and report any AE or SAE. SAEs may include: death, hospitalization due to worsening psychiatric symptoms or suicidal ideation, or all life threatening or disabling/incapacitating events among research participants. AEs may include, but are not limited to: physical injuries, worsened physical or mental health, or inadvertent disclosure of confidential research information.

If an SAE occurs, the PI will immediately contact the DSMB and IRB, followed by a written report in 24 hours. He will make a decision whether there is sufficient evidence to suspend data collection, allow for further IRB review, modify the protocol, or make other changes to reduce potential risk to participants. The study will resume based on agreement of the PI, the IRB chair, and the DSMB. In the event that an AE that is not an SAE is reported to the PI, the PI will discuss the event with the DSMB. Immediate evaluation will occur to determine if any extra steps can be taken to minimize the likelihood of that type of AE occurring again. If changes can be made, a report/amendment will be written and submitted to the DSMB and IRB.

As part of a standard practice, the PI will supervise the implementation of one audit within 4 months after study recruitment and one regularly per year afterwards of the materials collected and produced as part of the study at each site to ensure proper confidentiality and compliance with ethical principles, including confirmation of verbal consent, questionnaire data, and to make sure that the research staff are following established protocols. The PI will provide an annual summary report of all AEs to the IRB and the DSMB as part of the annual review. If no adverse events have occurred, the report will state, "No adverse events affecting human participants have occurred during this project year."

Data Monitoring. To ensure adequate participant recruitment and enrollment, each week, the PI will discuss the current number of participants contacted, screened, and enrolled from each site and compare those numbers to the expected based on our preliminary data. If after the first 4 months, it appears we are not reaching our expected number of participants, the PI will discuss potential barriers/obstacles and solutions with the research team and DSMB. Discussions regarding recruitment and enrollment will continue at each meeting with the DSMB to ensure proper implementation of the study.

Data Safety & Monitoring Board. The purpose of the DSMB is to review protocols and consent documents for this study, monitor safety issues throughout the study, provide an overview of the quality of the accumulating data, and provide guidance on interim analyses and stopping rules. The DSMB will be comprised of individuals appointed by the funder (VA Health Services Research & Development) and will have no direct involvement in the study or conflict of interest with the research team conducting the clinical trial. The DSMB responsibilities will include:

- (1) Protect the safety of the participants
- (2) Review, provide approval/disapproval, and provide suggestions to protocols, consent documents, and plans for data safety and monitoring.
- (3) Monitor, provide suggestions, and report on ethical issues regarding protection of human subjects, and advise on ethical issues regarding AEs. The DSMB will coordinate with the PI to report to the IRB any unanticipated problems involving risk. The DSMB will provide potential solutions or other appropriate actions (e.g., altering inclusion/exclusion criteria, changing consent documents).
- (4) Ensure appropriate balance between clinical care, safety, and patient confidentiality.
- (5) Monitor data the progress of the trial. The DSMB will periodically review outcome data for outcomes by treatment condition, including participant recruitment, retention, risks and benefits, and other factors that may affect outcomes. If differences in results

between conditions appear to be clinically significant, the DSMB will review whether the clinical trial should continue with or without further enrollment of new participants.

- (6) Monitor and review any data relevant to quality control and safety.
- (7) Make recommendations to the HSR&D about the continuation, termination, or changes to the trial based on benefits or adverse effects of the treatment.
- (8) Communicate problems with the conduct, enrollment, sample size, and/or data collection to HSR&D

The PI will convene annually with the DSMB for the duration of the study. The meetings will be held via video teleconference. The Board Chair and PI will decide on the format of the meetings. Additional meetings will be held on the recommendation of the Board Chair and PI and meeting logistics will be based on clinical urgency and the availability of the DSMB. The PI will submit reports to the DSMB a week prior to the scheduled meeting. Reports will include all data up to and including 2 weeks prior to the reporting deadline (except for SAEs, which are to be reported within 24 hours of an event). For each meeting at which the study is to be considered or monitored, the PI will present an overall progress statement containing the assurance that the PI has considered the clinical trial's progress and that there is/is not evidence of safety issues that should be addressed by the DSMB. The reports will also include information related to problems in recruitment, biases in attrition, biases with respect to AEs, or other operational problems that affect the integrity of the study. At the additional request of the DSMB, interim analyses will be conducted to determine whether the emerging findings may lead to a discussion of discontinuing the trial early.

The DSMB will be kept apprised of all SAEs and AEs on an ongoing basis and will decide whether individual patients should be removed from the protocol. Although research staff, under the PI's supervision, are able to take whatever immediate action is necessary to safeguard the welfare of individual patients, the DSMB will be called on whenever possible to make decisions as a result of a SAE. There may be rare instances where some unanticipated situations occur that may affect participant welfare. In these situations, the Syracuse VAMC IRB or the DSMB may be contacted to help resolve the situation.

Adverse Events (AE). AEs may include, but are not limited to: worsened physical or mental health, or inadvertent disclosure of confidential research information. Serious Adverse Events (SAE) may include: death, hospitalization due to worsening psychiatric symptoms or suicidal ideation, or all life threatening or disabling/incapacitating events among research participants. Per IRB regulations, SAEs, any event resulting in a deviation from the study protocol (e.g., emergency hospitalization to address suicidal behaviors) or death will be reported to the PI within 24 hours and to the IRB in 48 hours. This will be completed in order to assess significance and determine an appropriate response. AEs that involve temporary distress will be noted by interviewers and provided to the IRB in an annual report.

Confidentiality of Records. Numerous protections are in place to reduce the likelihood of loss of confidentiality. All research data will be kept in locked filing cabinets in secure areas, absent of identifying information, and coded by research number only. Files containing items with identifying information will also be kept in locked filing cabinets, but these will be separate from cabinets containing data from this study. All electronic files, including therapy notes, will be maintained on a secure study folder behind the VA firewall. Only approved study team personnel will be granted access to this data. All identifiable information will be stored in a separate folder behind the firewall from the de-identified study ID and data.

Potential Benefits of Research to Participants and Others. There may be direct and/or indirect benefits of study participation. Participants are receiving a brief intervention that

addresses a transdiagnostic factor that may reduce both loneliness and substance use. Because this intervention can be used for both participants who are not engaged in treatment and for participants who are engaged in treatment, it may augment current services. Dissemination of the findings from the study will contribute to the extant literature, provide data to guide implementation, and may contribute to reducing loneliness and substance use.

Importance of Knowledge to be Gained. Understanding how to effectively address loneliness among Veterans with SUD is a critical approach to curb substance-related morbidity and mortality. Loneliness is associated with increased suicide risk, substance use, and key precipitants to relapse among people addicted to substances. Addressing loneliness has the potential to reduce substance use. The proposed study tests the 8-session CBT-L/SUD that will be refined as part of this study. This telehealth intervention targets cognitive biases, and avoidance of social interactions and enjoyable activities. We expect that this intervention will reduce loneliness, increase the quality and quantity of social interactions, and reduce substance use. Knowledge gleaned from this study will help inform a fully powered randomized clinical trial with the long-term goal of future implementation and dissemination efforts across numerous settings.

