5.4 Inclusion/Exclusion Criteria

Inclusion criteria: Participants will include men and women who:

- Are English-speaking
- Are 18 years of age or older
- Have access to a phone or computer
- Screen positive for active SUD of at least moderate severity based on the M.I.N.I.
- Screen positive for loneliness by scoring at least a T-score > 60 on the NIH Toolbox loneliness scale

We will use the Veteran Verification screening for Veterans recruited through social media advertising to help confirm Veteran status.

Exclusion: Veterans will be excluded on the basis of:

- Does not understand informed consent

Pregnant women will not be excluded from this study as no invasive medical procedures are being performed and there is no known risk to the mother or the fetus of the proposed interventions. The study will not include prisoners or institutionalized Veterans.

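### The session-start address question is written only for participants whose sole phone is a cell phone; it should be asked of everyone at every contact

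*Combined protocol and SAP*

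**What the plan says.** The relevant text is under Protection Against Risk in section 6.0 of the combined protocol and SAP. It starts from a realistic premise: "It is possible that participants may refuse to be transferred to the Crisis Line or hang up".

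Two location measures follow.

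- **Landline.** The plan says that "participants will be asked to use a landline so that the number can be tracked to an address if emergency services are needed".
- **Address question.** The next sentence opens "For participants who only have a cell phone" and continues, after a break in the text, "Interviewers will begin each session by asking the participant for the address from which they are calling". The stated purpose is that the clinician can send help.

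Two back-up measures are also written.

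- Directly after the address question: "Because participants may give a false address, clinicians will consult with Lifeline responders who have a protocol for emergency responses for cell phone callers".
- Slightly earlier, in the description of transfers to the hotline: "Hotline responders are well trained in emergency procedures and have working protocols for locating callers and initiating rescues".

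On the mode of contact, section 5.1 calls the intervention sessions phone-based, and 6.0 speaks of telephone sessions ("All telephone sessions will be conducted using protocols"). The CBT-L/SUD description in 5.1 says telehealth without naming a device, and 5.4 lists "Have access to a phone or computer" as an inclusion criterion. Sections 4.0, 5.1 and 6.0 put screening, consent and assessments on the telephone.

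**The concern.** The address question depends on which phone a participant owns, whereas the location problem depends on the device in use at that contact. The two usually agree, but they need not. Because the landline is a request and not a condition, someone who has one may still take a session on a cell phone. That person's call cannot be traced through the landline, and the trigger for the question is not met.

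What is at stake is participant safety, not inference. The protocol itself links loneliness to suicidal ideation, suicide attempts and suicide risk (sections 2.0 and 6.0), and every participant must screen positive for both loneliness and an active substance use disorder (5.4). Recruitment is nationwide, so staff cannot assume where someone is during a call, and contact details given at enrolment do not settle it. The plan already treats a current address as worth asking for; the wording leaves some contacts without it. Sample size, analyses and feasibility measures are unaffected.

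**Working it through.** The plan gives no figure to reproduce. The check is a reading of coverage by case, followed by the cost of the remedy.

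**Reading the split sentence.** The clause "For participants who only have a cell phone" ends in a comma at a break, and the text resumes with a capitalised word at "Interviewers will begin each session by asking the participant for the address from which they are calling". Read together they make one complete sentence, and the sentence after it is about cell phone callers, which supports that reading.

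**Coverage under that reading.**

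1. Participant uses a landline: the number can be traced to an address. Covered.
2. Participant whose sole phone is a cell phone, on that phone: address asked at each session, plus Lifeline consultation. Covered.
3. Landline owner on a cell phone: the landline cannot be used for tracing and the question is not triggered. Back-ups only.
4. Participant whose sole phone is a cell phone, on a computer: the question is still triggered, because it depends on ownership and applies at each session. Covered.
5. Landline owner, or someone with no phone, on a computer: no question is triggered, and only the hotline's general locating protocols remain. This case arises only if computer sessions are allowed.

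**What the back-ups supply.** Lifeline consultation is introduced because an address already given may be false, so it supplements the question. The hotline's locating protocols are described around a transfer, whereas the case at issue is a participant who refuses transfer or disconnects. The warm-transfer steps pass on the participant's risk, name and phone number, but no address.

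**Cost of asking everyone.**

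- Intervention sessions: 8 per participant (5.1, both treatments) x 36 participants (4.0, 5.2) = 288.
- Assessments (5.6): 2 x 6 in the one-arm trial + 3 x 30 in the randomized trial = 12 + 90 = 102.
- Planned contacts after screening: 288 + 102 = 390.
- Time per question: assumed 15 to 60 seconds; the documents give no figure.
- Low end: 390 x 15 / 3600 = 1.6 hours. High end: 390 x 60 / 3600 = 6.5 hours.
- Section 5.1 also mentions a mid-treatment assessment that the 5.6 schedule does not list. If it is run for all 36: 390 + 36 = 426 contacts, so 426 x 15 / 3600 = 1.8 hours to 426 x 60 / 3600 = 7.1 hours.

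These totals overstate the added time, because the question is already planned at sessions for participants whose sole phone is a cell phone.

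**The case against.** The strongest reply is that a location procedure exists in every case. The hotline's locating protocols carry no device limit, and the Lifeline protocol for cell phone callers describes exactly the landline owner on a cell phone. This stands against one tempting inference: a reader might conclude that such a participant has no written location step at all. The documents do not support that. What is missing is the question at the start of the contact; weaker measures are present.

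A second tempting inference is that every session taken by computer is uncovered. That also fails. A participant whose sole phone is a cell phone is asked at each session, whatever the device. Nor are computer sessions established: 5.1 calls the sessions phone-based, telehealth is compatible with a telephone, and the computer in 5.4 could relate to the online landing page and entry form. The computer case is therefore only conditional.

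Third, the key sentence is broken in the text. If its second half stood alone, the question would apply to everyone and the point would fall. The joined reading is the likelier one, but it is not certain.

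Finally, the screening script, the protocols for telephone sessions and the treatment manuals are not in the reviewed text, and staff receive suicide-risk training. A universal location question may already be in those materials. That limits confidence, but does not change what 6.0 says.

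**Conclusion.** The point holds in a narrow form. Followed exactly, section 6.0 does not have staff ask a landline owner who is using a cell phone where they are, and the same applies on a computer if such sessions are permitted. In those contacts the plan falls back on measures designed for a false address or for a transfer in progress.

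The number affected is unknown and probably small: the documents give no count of landline owners who will use a cell phone, or of computer sessions. The conclusion rests on reading the broken sentence as one, and on the operational scripts not already containing the question. Severity is minor. This is a cheap safety improvement, not a flaw in the design or analysis.

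**What to change.** In section 6.0, with sponsor and IRB agreement, replace the ownership trigger with one rule, for example: *At the start of every session and assessment, staff will ask every participant, whatever device is in use, for the address where they are at that moment.* Keep the landline request and the Lifeline consultation as they stand.

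The cost is one sentence of protocol text and, on the assumption above, a few seconds to a minute per contact, or 1.6 to 6.5 staff hours over the whole study. If the scripts already ask everyone, the change only brings 6.0 into line with practice. Eligibility wording need not change for this purpose.

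### The suicide-risk procedure sets no clear response for risk that is serious but not imminent: read plainly, it receives the low-acute-risk plan, with no safety plan required

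*Combined protocol and SAP*

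**What the plan says.** Section 6.0, under Protection Against Risk, has an interviewer who is worried about suicidal thinking ask two questions. The first concerns desire ("Do you have a desire to kill yourself that you think you might act on"); the second concerns a plan held with intent ("Do you have a plan for killing yourself and intend to carry the plan out"). The interviewer then grades severity from the answers and from whatever suicide measures are available. A finding of imminent risk brings a safety plan and emergency procedures. A neighbouring sentence offers Lifeline transfer to people found to be at risk, without repeating the word imminent.

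The lower level comes next: "For participants that have a lower risk than imminent for suicide at baseline, our crisis plan will be consistent with guidelines employed by" a source whose name is masked, "as well as by the DoD/VA for people at low acute risk for suicide". The steps that follow are ones "which may or may not already be in place at the time the participant is deemed at low acute risk". They begin "1) consider consultation with behavioral health specialty, (2) discuss safety and restriction of access to lethal means" and continue "3) treat mental health and medical conditions, (4) address psychosocial needs, (5) encourage social support". The last two are to "continue monitoring patient status and reassess risk in follow-up contacts" and to document the risk assessment.

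**The concern.** The entry condition for the lower level is any risk short of imminent, but the standard applied there is the one for low acute risk. Those two groups are not the same. A Veteran can report a desire that might be acted on, deny a plan with intent, and be judged serious but not imminent. The protocol's own two questions make that answer pattern foreseeable, yet no response is written for it other than the low-risk one.

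What is at stake is participant safety. The Introduction (2.0) reports more suicide attempts among people with substance use disorders who are lonely than among those who are not, and this is the group being enrolled. Section 5.4 has no exclusion for suicide risk. Assessments are by phone and recruitment is nationwide, so staff depend on the written procedure more than they would in a clinic.

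**Working it through.** The plan gives no figure to reproduce, so the check compares the provisions of section 6.0 and searches the rest of the document for anything that fills the space between them.

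1. **Response at imminent risk.** Safety plan, emergency procedures and warm transfer to the crisis line.
2. **Response below imminent.** The seven-item list, tied to low acute risk. Of the 7 items, 1 (specialty consultation) is only to be considered and 7 − 1 = 6 are stated without that qualifier. None is a safety plan; the nearest is item 2, a discussion of safety and access to lethal means.
3. **Levels with a written response.** Imminent + low acute = 2. No section names a level between them, and a safety plan is mentioned only in connection with imminent risk.
4. **Two readings of the lower-level sentence.** (a) Everyone below imminent enters the seven-item plan, so serious non-imminent risk is handled as low risk. (b) The phrase about being deemed at low acute risk is a separate judgement, so those above low and below imminent have no written response. The gap exists under both.
5. **Size.** Two yes/no questions give 2 × 2 = 4 answer patterns, and 4 − 1 = 3 contain at least one yes. How many fall short of imminent depends on a threshold the protocol does not give. Taking the two answers alone, and assuming three possible rules:
   - both answers must be yes: 3 − 1 = 2 patterns fall short;
   - yes to the second question is needed: 3 − 2 = 1;
   - any yes is enough: 3 − 3 = 0.

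   The range of 0 to 2 of 3 shows only that the rule is undetermined. It does not measure risk or count participants, and the value 2 includes an implausible pattern (an intended plan without a desire that might be acted on). In practice the interviewer also uses other suicide measures, which are not named; the schedules in 5.6 list no suicide-specific one.
6. **Timing.** The lower-level sentence is limited to baseline. Taken literally, non-imminent risk first found later has no stated plan. Against that, the two questions apply at assessments generally, and the sixth item looks ahead to later contacts, so wider coverage was probably meant.

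**The case against.** The strongest reply is that the text is unclear rather than unsafe. Imminent risk is a judgement, and a Veteran who endorses a desire that might be acted on could well be rated imminent. One guideline source is masked, and the low-acute-risk qualifier may attach only to the DoD/VA guideline. The Lifeline sentence drops the word imminent, which may mean that it reaches this group.

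The safeguards are also substantial. Supervision of all work by a licensed clinician is mandatory. Staff are trained and tested in risk assessment. Reassessment at follow-up contacts would take place within 8 weekly sessions during treatment. Staff may take immediate action to protect a participant (Data Safety & Monitoring Plan), and the investigator may withdraw someone (5.8).

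Much of this stands. A reader might infer that every participant below imminent risk is in fact managed as low risk, or that serious risk goes unaddressed. The documents do not support that: the threshold is undefined, the sentence is limited to baseline, the masked source cannot be seen, and the seven items have real content.

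The safeguards still do not supply the missing rule. The timing of clinician review is not stated. The transfer offer directly follows a sentence confined to imminent risk, so its reach is uncertain. Immediate action and withdrawal are discretionary. Reassessment thins out after treatment: the next scheduled assessment after the post-intervention one is at 30 days in the randomized trial, and there is none in the one-arm trial.

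**Conclusion.** The point holds as a gap in the written procedure. Serious but non-imminent risk receives either a low-risk plan without a required safety plan or, on the alternative reading, no written response. The number of participants concerned is unknown and cannot be derived from the documents. The conclusion rests on the visible text of section 6.0 and assumes that the masked source does not add an intermediate level; the content of the DoD/VA guideline was not used. No analysis or sample-size figure is affected. This is a cheap improvement: the current wording leaves two interviewers free to respond differently to the same answers, and staff, supervision and the transfer route are already in place.

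**What to change.** Amend section 6.0, Protection Against Risk, in three places:

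1. Limit the seven-item plan to participants judged at low acute risk. For anyone above low but not imminent (at minimum, any yes to the first follow-up question that is not rated imminent), require a safety plan, an offered Lifeline transfer and review by the supervising licensed clinician already on the study. This can be a separate intermediate level or a lower threshold for the existing response. The investigators, IRB and DSMB should confirm the content and the time limit for review, since the protocol states no clinical standard for this group.
2. Delete the restriction to baseline, so that the rule covers every assessment and session.
3. State which risk level the Lifeline transfer offer applies to.

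The cost is a protocol wording amendment, a small addition to training already planned, and some supervising-clinician time. No participants or assessments are added.
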